7.3 LOST TO FOLLOW-UP

A participant will be considered lost to follow-up if he or she fails to return for one study visit and is unable to be contacted by the study site staff.

The following actions must be taken if a participant fails to return to the clinic for a required study visit:

- The site will attempt to contact the participant and reschedule the missed visit within a one week window of the missed visit and counsel the participant on the importance of maintaining the assigned visit schedule and ascertain if the participant wishes to and/or should continue in the study.
- Before a participant is deemed lost to follow-up, the investigator or designee will make every effort to regain contact with the participant (where possible, 3 telephone calls and, if necessary, a certified letter to the participant's last known mailing address or local equivalent methods). These contact attempts should be documented in the participant's medical record or study file.
- Should the participant continue to be unreachable, he or she will be considered to have withdrawn from the study with a primary reason of lost to follow-up.

8 STUDY ASSESSMENTS AND PROCEDURES

8.1 EFFECTIVENESS ASSESSMENTS

Effectiveness assessments will include the following instruments:

- Impairment Rating Scale
- ADHD-RS-IV
- CGI-I
- TOVA-9
- ToSREC
- MFaCTs

Every effort must be made to ensure that raters of all rating scales/assessments are kept consistent among participants throughout trial participation. Each rating scale/assessment for the participant should be administered by the same rater for the duration of the trial. If a rater leaves a clinical site for any reason the site should replace the rater as quickly as possible, and this replacement rater will also be expected to complete rater training (if not previously trained). The replacement rater should review the participant's source documents for previously completed rating assessments, in an effort to become familiar with the former rater's evaluations.

8.2 SAFETY AND OTHER ASSESSMENTS

Safety assessments will include the evaluation of adverse device events (ADEs).

8.3 ADVERSE DEVICE EFFECTS, SEVERITY, AND REPORTING

8.3.1 DEFINITION OF ADVERSE DEVICE EFFECTS (ADE)

An ADE is an adverse event related to the use of an investigational medical device. This includes any adverse event resulting from insufficiencies or inadequacies in the instructions for use, the deployment, the implementation, the installation, the operation, or any malfunction of the investigational medical device. This also includes any event that is a result of a user error or intentional misuse.

8.3.2 DEFINITION OF UNANTICIPATED ADVERSE DEVICE EFFECTS (UADE)

Per 21 CFR 812.3, an Unanticipated Adverse Device Effect is any serious adverse effect on health or safety or any life-threatening problem or death caused by, or associated with, a device, if that effect, problem, or death was not previously identified in nature, severity, or degree of incidence in the investigational plan or application (including a supplementary plan or application), or any other unanticipated serious problem associated with a device that relates to the rights, safety, or welfare of participants.

Unanticipated Adverse Device Effects will include events meeting BOTH A and B as stated below:

A. Events meeting ALL of the following criteria:

1) Not included in the list of Anticipated Events (refer to protocol Section 8.3.3)

2) Possibly, probably, or definitely related to the investigational device (per the sponsor)

B. Serious (meets any of the following criteria):

- 1) Is life-threatening illness or injury
- 2) Results in permanent impairment of a body structure or a body structure
- 3) Necessitates medical or surgical intervention to prevent permanent* impairment of a body function or a body structure. (***Permanent*** is defined as irreversible impairment or damage to a body structure or function, excluding trivial impairment or damage)
- 4) Leads to fetal distress, fetal death or a congenital abnormality or birth defect
- 5) Leads to death.

8.3.3 PREVIOUSLY KNOWN ADVERSE DEVICE EFFECTS

AKL-T01 (instructions for use)....The expectedness of an ADE shall be determined according to the specified reference document containing safety information (e.g., Instructions for Use) and the expected ADEs listed below. Any ADE that is not identified in nature, severity, or specificity in the current investigational product reference documents is considered unanticipated.

Adverse Device Effects expected for this device are as follows:

- Dizziness
- Nausea
- Headache
- Decreased frustration tolerance
- Emotional reaction

8.3.4 CLASSIFICATION OF AN ADVERSE DEVICE EFFECTS

8.3.4.1 SEVERITY OF EVENT

The following guidelines will be used to describe the severity of an ADE:

- **Mild:** Awareness of sign, symptom, or event, but easily tolerated.
- **Moderate:** Discomfort enough to cause interference with usual activity and may warrant intervention.
- **Severe:** Incapacitating, with an inability to do usual activities or significantly affects clinical status and warrants intervention. **Please note: the term “severe” is not the same as “serious”.**

8.3.4.2 RELATIONSHIP TO STUDY TREATMENT

All ADEs must have their relationship to study treatment assessed by the clinician who examines and evaluates the participant based on temporal relationship and his/her clinical judgment. In a clinical trial, the investigational device must always be suspect. The degree of certainty of causal relationship of an adverse device effect of either study treatment will be rated as follows:

- **Possible:** An event that might be due to the use of the study device. An alternative explanation - e.g., concomitant drug(s), concomitant disease(s) - is inconclusive. The relationship in time is reasonable; therefore the causal relationship cannot be excluded.
- **Probable:** An event that might be due to the use of the study device. An alternative explanation is less likely - e.g., concomitant drug(s), concomitant disease(s). The relationship in time is suggestive.
- **Definitely:** An event that is due to the use of the study device. The event cannot be reasonably explained by an alternative explanation - e.g., concomitant drug(s), concomitant disease(s).

8.3.4.3 EXPECTEDNESS

The DCRI Safety Medical Monitor will be responsible for determining whether an ADE is expected or unexpected for events meeting serious criteria. An ADE will be considered unexpected if the nature, severity, or frequency of the event is not consistent with the risk information previously described for the study treatment.

8.3.5 TIME PERIOD AND FREQUENCY FOR EVENT ASSESSMENT AND FOLLOW-UP

The occurrence of an ADE may come to the attention of study personnel during study visits and interviews of a study participant presenting for medical care, or upon review by a study monitor.

All ADEs including local and systemic reactions will be captured on the appropriate case report form (CRF). Information to be collected includes the event description, time of onset, clinician's assessment of severity, relationship to study product (assessed only by those with the training and authority to make a diagnosis), and time of resolution/stabilization of the event. All ADEs occurring while in the study will be documented appropriately regardless of relationship. All ADEs will be followed to adequate resolution.

Any medical condition that is present at the time that the participant is screened will be considered as baseline and not reported as an ADE. However, if the study participant's condition deteriorates at any time during the study, it will be recorded as an ADE.

Changes in the severity of an AE will be documented to allow an assessment of the duration of the event at each level of severity to be performed. ADEs characterized as intermittent require documentation of onset and duration of each episode.

The Site Principal Investigator will record all reportable events with start dates occurring from the time of enrollment through the final study visit (Day 84). At each study visit, the investigator will inquire about the occurrence of ADEs since the last visit. Events will be followed for outcome information until resolution or stabilization.

8.3.6 ADVERSE DEVICE EFFECTS REPORTING

It is understood that complete information about an event may not be known at the time the initial report is submitted. The investigator must assess the relationship of the event to the investigational

device (including rationale for assessment) and should make every attempt to obtain as much information as possible concerning the event. Additional information pertaining to an event should be reported in the EDC as it becomes available.

The investigator must report, via IBM Clinical Development EDC database, all adverse device effects (anticipated or unanticipated) that meet serious criteria occurring from the time of enrollment through the final study visit (Day 84) within 24 hours of knowledge of the event. If the EDC database is temporarily unavailable, the event, including investigator-determined causality assessment, should be reported to DCRI via a paper back-up ADE form. Upon return of the availability of the EDC database, the ADE information must be entered into the eCRF.

The investigator must report, via IBM Clinical Development EDC database, when important follow-up information (final diagnosis, outcome, results of specific investigations, etc.) becomes available after submission of the initial ADE form and information. Follow-up information should be submitted according to the same process used for reporting the initial event as described above (i.e., within 24 hours of knowledge, via IBM Clinical Development EDC database). All adverse device effects will be followed through resolution.

DCRI Safety Surveillance will report all adverse device effects to specified trial personnel (sponsor, protocol principal investigator [PI] and project leader) within 1 to 2 business days of receipt.

8.4 UNANTICIPATED PROBLEMS

8.4.1 DEFINITION OF UNANTICIPATED PROBLEMS (UP)

The Office for Human Research Protections (OHRP) considers unanticipated problems involving risks to participants or others to include, in general, any incident, experience, or outcome that meets all of the following criteria:

- Unexpected in terms of nature, severity, or frequency given (a) the research procedures that are described in the protocol-related documents, such as the IRB-approved research protocol and informed consent document; and (b) the characteristics of the participant population being studied
- Related or possibly related to participation in the research ("possibly related" means there is a reasonable possibility that the incident, experience, or outcome may have been caused by the procedures involved in the research)
- Suggests that the research places participants or others at a greater risk of harm (including physical, psychological, economic, or social harm) than was previously known or recognized.
- Unanticipated adverse device effect, any serious adverse effect on health or safety or any life-threatening problem or death caused by, or associated with, a device, if that effect, problem, or death was not previously identified in nature, severity, or degree of incidence in the investigational plan or application (including a supplementary plan or application), or any other unanticipated serious problem associated with a device that relates to the rights, safety, or welfare of participants
- Examples of potential Unanticipated Problems include, but are not limited to:

- 1) Unanticipated misuse of device hardware
- 2) Unanticipated misuse of device software
- 3) Unanticipated hardware issues
- 4) Unanticipated software issues.

8.4.2 UNANTICIPATED PROBLEM REPORTING

The investigator will report unanticipated problems (UPs) to the reviewing IRB and to the DCRI Safety Surveillance/lead principal investigator (PI). The UP report will include the following information:

- Protocol-identifying information: protocol title and number, PI's name, and the IRB project number
- Detailed description of the event, incident, experience, or outcome
- Explanation of the basis for determining that the event, incident, experience, or outcome represents an UP
- Description of any changes to the protocol or other corrective actions that have been taken or are proposed in response to the UP.

An investigator shall submit to the sponsor and to the reviewing IRB a report of any unanticipated device problem occurring during an investigation as soon as possible, but in no event later than 10 business days after the investigator first learns of the effect. A sponsor who conducts an evaluation of an unanticipated adverse device effect under 812.46(b) shall report the results of such evaluation to the Food and Drug Administration (FDA) and to all reviewing IRBs and participating investigators within 10 business days after the sponsor first receives notice of the effect. Thereafter, the sponsor shall submit such additional reports concerning the effect as FDA requests.

9 STATISTICAL CONSIDERATIONS

This section provides a brief overview of the statistical analyses, both quantitative and qualitative in nature that will be used during this study. In addition to what follows in this section, further details will be provided in a separate statistical analysis plan (SAP).

The primary objectives of this study are to (1) understand the synergistic impairment effects when combining AKL-T01 (with app-based symptom tracking, AKL-X01) as adjunctive treatment to stimulant medication, and (2) understand the impairment effects of AKL-T01 (with app-based symptom tracking, AKL-X01) treatment in participants not recently on stimulant medication. Within both the medicated and non-medicated cohorts, a change in Impairment Rating Scale (IRS) (Clinician Report) from baseline to Day 28 will demonstrate the overall effect that AKL-T01 treatment has on ADHD symptoms.

The secondary objective of this study is to understand the symptom and attentional effects of AKL-T01 (with app-based symptom tracking AKL-X01) treatment in all participants. There is an additional exploratory objective which focuses specifically on sustained benefits, through reduction of ADHD symptoms and impairment, experienced by participants following (a) 1-month of treatment with AKL-T01, and (b) an additional 4 weeks of AKL-T01 treatment.

9.1 STATISTICAL HYPOTHESES

The aim of the primary objective is to demonstrate a statistically significant difference on mean change in IRS “Overall severity of child’s problem in functioning and overall need for treatment” score, defined for each participant as the score measured on Day 28 minus the score measured at the baseline visit. In both the medicated and non-medicated cohorts, the statistical significance of the primary efficacy analysis will be assessed using a 2-sided paired *t*-test evaluated at the 95% level of confidence. The formulation of the null (H_0) and alternative (H_a) hypotheses are stated below, where μ_d refers to the true mean difference:

- $H_0: \mu_d = 0$
- $H_a: \mu_d \neq 0$.

If, within a particular cohort, the upper bound of the 95% confidence interval around the sample difference is smaller than 0, we will have sufficient evidence to reject H_0 and conclude that AKL-T01 plus Fengo improves ADHD symptoms in that cohort.

If the set of sample differences is non-normal, defined here as skewness larger than 1.5 in magnitude, the efficacy analysis will proceed as a non-parametric Wilcoxon signed rank test. Significance will be determined by evaluating the *W*-statistic at the 95% level of confidence.

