3 OBJECTIVES AND ENDPOINTS

OBJECTIVES	ENDPOINTS	JUSTIFICATION FOR ENDPOINTS
Primary		

Cohort 1: To understand the synergistic impairment effects when combining AKL-T01 (with AKL-X01 symptom tracking) as adjunctive treatment to stimulant medication.
 
Cohort 2: To understand the impairment effects of AKL-T01 (with AKL-X01 symptom tracking) treatment in participants not recently on stimulant medication.
	
Cohort 1, Cohort 2:
 
 1) Overall change in clinician-reported Impairment Rating Scale (IRS) "Overall severity of child's problem in functioning and overall need for treatment" score from baseline to Day 28. 	
Cohort 1: The overall change in Impairment Rating Scale (Clinician Report) from baseline to Day 28, in participants on stimulant medication, will demonstrate the overall effect that AKL-T01 has on ADHD related impairments when administered in addition to stimulant medication. The IRS score measures the effects on individualized functional impairments.
 
Cohort 2: The overall change in IRS (Clinician Report) from baseline to Day 28, in participants not currently on stimulant medication, will demonstrate the overall effect that AKL-T01 has on ADHD related impairments when administered without stimulant medication. The IRS score measures the effects on individualized functional impairments.

Secondary		
To understand symptom and attentional effects of AKL-T01 (with AKL-X01 symptom tracking) in all participants (both Cohort 1 and Cohort 2).	
Cohort 1, Cohort 2:
 
 1) Overall change in ADHD-Rating Scale (ADHD-RS) total component score from baseline to Day 28. 2) Clinical Global Impression-Improvement (CGI-I) score at Day 28. 3) Overall change in Test of Variable Attention-Version 9 (TOVA) attention composite score (ACS) and certain constituent scores, from baseline to Day 28 (the specific constituent scores will be described in the SAP). 	Measuring and analyzing the overall change in ADHD-Rating Scale and Test of Variable Attention-Version 9 from baseline to Day 28, and the Clinical Global Impression – Improvement score at Day 28, will assist with assessing the impact of AKL-T01 on ADHD symptoms within the short-term following treatment administration.

OBJECTIVES	ENDPOINTS	JUSTIFICATION FOR ENDPOINTS

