4 STUDY DESIGN

4.1 OVERALL DESIGN

This study is a multi-center, open label trial to determine the effect of AKL-T01 treatment (with AKL-X01 mobile app-based symptom tracking) on ADHD symptoms and impairments in children currently on or off stimulant.

Two hundred and three participants (203) at multiple sites will be enrolled into 2 cohorts. 130 participants will be recruited into cohort 1 and 73 participants will be recruited into cohort 2.

Cohort 1 will have been stable** on stimulant(s) for at least 30 days before baseline. At screening (at least 7 and up to 30 days before baseline), participant caregivers will be instructed to download AKL-X01 on to their smartphone. Caregivers will use AKL-X01 for tracking participants' symptoms and behaviors beginning between days -30 and -7, through day 84. During Treatment Phase 1, Days 1 through 28, participants will continue receiving stimulant and will also receive AKL-T01 treatment. During the 1-month treatment pause, Days 29 through 56, participants will continue receiving stimulant but will discontinue AKL-T01. During Treatment Phase 2, Days 57 through 84, participants will continue receiving stimulant and will also receive AKL-T01 treatment.

****Note:** Medication stability is defined as:

- Moderate response on stimulant, but still room for improvement
- Dose unchanged within past 30 days, but other doses have been tried previously without improvement
- Currently taking stimulant, but parent and/or caregiver wishes not to increase dosage for any reason
- Taking consistent stimulant dose on weekdays, but not on weekends

The hypothesis for Cohort 1 is that children receiving stimulant plus AKL-T01 treatment will improve in ADHD symptoms and impairments from Day 0 to Day 28.

Cohort 2 will have been stable without any stimulant for ≥ 30 days before baseline. At screening (at least 7 and up to 30 days before baseline), participant caregivers will be instructed to download AKL-X01 on to their smartphone. Caregivers will use AKL-X01 for tracking participant symptoms and behaviors beginning between days -30 and -7, through day 84. During Treatment Phase 1, Days 1 through 28, participants will receive AKL-T01 treatment. During the 1-month treatment pause, Days 29 through 56, participants will discontinue AKL-T01. During Treatment Phase 2, Days 57 through 84, participants will receive AKL-T01 treatment.

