9.4.2 ANALYSIS OF THE PRIMARY EFFICACY ENDPOINT(S)

The primary efficacy endpoint for each participant is the change in IRS score from baseline to Day 28, defined as the score on Day 28 minus the score at baseline. Missing data will not be imputed. If a participant is missing either the baseline or Day 28 IRS assessment, that participant will be excluded from the analysis. Within each cohort, the ITT population is the primary efficacy analysis population. Additional per-protocol analyses will be performed on the per-protocol population.

Statistical significance of the change in IRS will be determined using a paired *t*-test. No adjustment for covariates will take place for the primary efficacy analysis, although additional analyses may be requested at the discretion of the investigators. Details will be provided in the SAP.

The results of the primary efficacy analysis will be summarized by cohort as mean change (95% confidence interval) and p-value. If the upper bound of the 95% confidence interval is smaller than 0 in a particular cohort, we will conclude that significance is achieved within that cohort.

Outliers will be determined clinically and identified by an independent third party, with confirmation coming from the PI. If outliers are identified for a given endpoint, a sensitivity analysis will be performed without the outlier.

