9.4.3 ANALYSIS OF THE SECONDARY ENDPOINT(S)

The following secondary efficacy endpoints will be tested using the same technique outlined for the primary efficacy analysis: (1) change in sum of ADHD-RS component scores from baseline to Day 28; (2) CGI-I score at Day 28; and, (3) change in TOVA ACS and certain constituents, from baseline to Day 28. The ITT population will be used for all secondary efficacy endpoints with the same analyses being repeated on the per-protocol population.

Family-wise error rate will be controlled using a hierarchical testing strategy. Within each cohort, the maximum allowable Type I error rate will be set to 0.05.

If the primary efficacy endpoint is significant at the 0.05 confidence level, the secondary efficacy endpoints will be tested sequentially in the order in which they appear above, starting with (1) change in autocalculated sum of ADHD-RS Total. If the test for (1) is significant at the 0.05 confidence level, the test for (2) CGI-I score at Day 28 will proceed. If the test for (2) is significant at the 0.05 confidence level, the test for (3) change in TOVA constituents from baseline to Day 28 will proceed, starting with Ex-Gaussian Tau Total, and then to API/ACS, Commission Errors Standard Score H2, RT Variability Standard Score Total, RT Mean Standard Score H1, D-Prime Standard Score H2, and Omission Errors Standard Score H2, in this order. At any point, if the test of a secondary efficacy endpoint fails to achieve significance at the 0.05 confidence level, only nominal p-values will be reported for that endpoint and for all subsequent secondary efficacy endpoints.

If the primary efficacy endpoint is not significant at the 0.05 confidence level, only nominal p-values will be reported for all secondary efficacy endpoints.

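### Section 9.1 turns a significant fall in one open-label impairment rating into the conclusion that the product improves ADHD symptoms; it should claim only that rated impairment fell

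*Combined protocol and SAP*

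**What the plan says.** - **Section 9.1** sets a two-sided paired t-test, per cohort, on the change in the IRS overall-severity item from baseline to Day 28. If the upper bound of the 95% interval is below 0, the plan will "conclude that AKL-T01 plus Fengo improves ADHD symptoms in that cohort". If skewness exceeds 1.5 in magnitude, a Wilcoxon signed-rank test replaces the t-test.
- **Section 9**, introductory text, says the IRS change "will demonstrate the overall effect that AKL-T01 treatment has on ADHD symptoms". The same text states both primary objectives in terms of impairment and puts symptoms in the secondary objective.
- **Section 3** says: "The IRS score measures the effects on individualized functional impairments". For Cohort 1 it describes the target as "ADHD related impairments when administered in addition to stimulant medication". Its secondary row gives the impact on symptoms to the ADHD-RS, the CGI-I and the TOVA.
- **Section 9.4.3** tests the secondary endpoints in a fixed order, only if the primary is significant, "starting with (1) change in autocalculated sum of ADHD-RS Total".
- **Section 9.4.2** applies the same confidence-interval criterion to the same endpoint and says only "we will conclude that significance is achieved within that cohort".
- **Section 4.1**: "This study is a multi-center, open label trial". Both cohorts receive AKL-T01, and section 9.4.1 plans comparisons within each cohort.
- **Sections 1.1, 3 and 9** call the Cohort 1 primary objective *synergistic*.

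**The concern.** The pre-specified conclusion goes beyond the test in two ways.

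*Construct.* An impairment item is read as evidence on symptoms. The plan has its own symptom endpoints and protects them with a testing order. The sentence in 9.1 bypasses that order, because the symptom claim is made as soon as the primary succeeds.

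*Cause.* The word *improves* attributes the change to the product. Rejecting a zero mean change in an uncontrolled group does not separate the product from time, rater or parent expectancy, or regression after selection. Section 5.1 selects children with sub-optimal status on the CGI-S, and the schedule of activities places the CGI-S at the same visit as the baseline clinician IRS. It also requires a parent IRS overall score of at least 3 at screening.

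At stake is what the trial may say if its primary test succeeds. A report that follows 9.1 literally would carry a causal symptom claim that the primary analysis cannot support.

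**Working it through.** **1. The plan's own figures.** Section 9.2 assumes SD 1, effects of 0.30 (Cohort 1) and 0.40 (Cohort 2), 90% power and two-sided 5%. With n = (SD × (z₀.₉₇₅ + z₀.₉₀) / δ)²:
- Cohort 1: ((1.960 + 1.282) / 0.30)² = 116.75, so 117, as stated.
- Cohort 2: ((1.960 + 1.282) / 0.40)² = 65.67, so 66, as stated.

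Exact noncentral-t power at these sizes is 89.6% and 89.3%.

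**2. What triggers the 9.1 conclusion.** The smallest significant mean fall is t₀.₉₇₅,ₙ₋₁ × SD / √n. At SD 1 this is 0.183 points for n = 117 and 0.246 points for n = 66. Nothing else enters the rule: no symptom score and no comparator.

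**3. The sections side by side.** Section 3 gives impairment to the IRS and symptoms to the ADHD-RS, CGI-I and TOVA. Section 9.4.3 opens the symptom tests only after the IRS test succeeds. Section 9.1 makes the symptom statement at the IRS step. It therefore comes before every symptom test and does not depend on any of them. This holds without any numerical assumption.

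**4. Illustration: how often the label and the ADHD-RS could part.** The documents give no ADHD-RS effect and no correlation between the two changes, so both are assumed. The changes are bivariate normal with correlation 0.3, 0.5 or 0.7, the IRS effect is as designed, and each test requires t > t₀.₉₇₅,ₙ₋₁ in the improving direction (200,000 simulated trials per cell). The table gives the probability that the IRS rule is met and the ADHD-RS test fails.

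| ADHD-RS effect relative to IRS (SD units) | n = 117, correlation 0.3 / 0.5 / 0.7 | n = 66, correlation 0.3 / 0.5 / 0.7 |
|---|---|---|
| equal | 0.080 / 0.069 / 0.055 | 0.085 / 0.071 / 0.056 |
| half | 0.550 / 0.542 / 0.536 | 0.554 / 0.541 / 0.535 |
| zero | 0.872 / 0.872 / 0.872 | 0.868 / 0.869 / 0.869 |

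The last row is close to power × 0.975 (0.896 × 0.975 = 0.874; 0.893 × 0.975 = 0.871). It follows almost by construction and is not evidence about this trial.

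**5. Illustration: attribution.** Suppose the device has no effect and scores fall by δ for other reasons. The rule is met with probability P(T > t₀.₉₇₅,ₙ₋₁), where T is noncentral t with n − 1 degrees of freedom and noncentrality δ√n / SD.

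| Assumed fall | n = 117, SD 1 | n = 117, SD 2 | n = 66, SD 1 | n = 66, SD 2 |
|---|---|---|---|---|
| 0 | 0.025 | 0.025 | 0.025 | 0.025 |
| 0.1 | 0.187 | 0.077 | 0.123 | 0.059 |
| 0.2 | 0.574 | 0.187 | 0.360 | 0.123 |
| 0.3 | 0.896 | 0.363 | 0.670 | 0.224 |

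This is the design's own power curve under another label. The documents give no uncontrolled IRS change from which to choose a row.

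**The case against.** *Symptoms are a stated aim.* The hypothesis in section 4.1 is that children "will improve in ADHD symptoms and impairments from Day 0 to Day 28". That makes symptoms a legitimate study question. It does not make an impairment item the test of it, since sections 3 and 9.4.3 assign that to other endpoints.

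*Sections 9.1 and 9.4.2 are compatible.* A reader might infer that they give rival conclusions for one test. The documents do not support that. Section 9.4.2 says when significance is declared and is silent on interpretation; 9.1 adds the interpretation. The shared element is the confidence-interval criterion, and 9.4.2 does not repeat the Wilcoxon branch. The fault lies in the interpretation that 9.1 adds.

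*Naming Fengo is fair.* A reader might infer that, because tracking starts at least 7 days before baseline, Fengo cannot belong in the conclusion. That goes too far. The objectives define the regimen as AKL-T01 with AKL-X01 tracking, and tracking continues through Days 1 to 28. Its contribution cannot be separated, but it is part of what was used.

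*Other explanations are limited.* The plan asks for stable stimulant dosing and unchanged behavioural therapy, and asks sites to restrict raters' access to compliance data. Section 4.2 reports no significant within-group change in an earlier control arm (p = 0.67), and section 2.2 lists the IRS among the pivotal trial's assessments. All this helps. But the control-arm result is on the TOVA API in children not on stimulants, and no control-arm IRS change is given. The safeguards reduce non-specific change and do not replace a control.

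*Synergy.* A reader might infer that no comparison could ever address it. A Cohort 1 against Cohort 2 difference in change could be computed, but it would be non-randomised and confounded. What can be said is that the supplied text specifies no test of synergy.

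**Conclusion.** The point holds as a matter of wording and inference. The 9.1 conclusion and the matching sentence in section 9 name the wrong construct and attribute cause that an open-label, within-cohort comparison cannot establish. The construct fault rests on the documents' own text and needs no assumption. The attribution fault rests on the absence of a control.

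The size of either problem is not known. The illustrative ranges are 5.5% to 8.5% (equal effects) up to about 87% (no ADHD-RS effect) for a symptom claim with a failed ADHD-RS test. For the rule being met by an assumed non-specific fall of 0.1 to 0.3, they are 6% to 90% across the two cohorts and SD 1 to 2. A reader might take these as estimates of harm. They are not: they depend on effects, correlations and falls that the documents do not give. Nor does the point imply that AKL-T01 lacks an effect, or that the sample size or testing order is wrong. It should be corrected because it governs what a positive primary result may be said to mean.

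**What to change.** 1. In 9.1 and the introductory text of section 9, replace the symptom conclusion with: *mean clinician-rated IRS impairment fell from baseline to Day 28 in this cohort during open-label use of AKL-T01 with AKL-X01 tracking*. Give the signed-rank equivalent for use when the Wilcoxon branch applies.
2. Leave statements about symptoms to the gated secondary endpoints that section 3 assigns to them (ADHD-RS, CGI-I and TOVA), with the same caveat that the comparison is uncontrolled.
3. Add that caveat to the causal wording in section 2.1 (final paragraph) and in the section 3 justifications for both cohorts. These name impairment correctly but still credit the device with the change. Aligning 9.1 with 9.4.2 alone would leave them untouched.
4. In sections 1.1, 3 and 9, replace *synergistic* with wording such as *change when AKL-T01 is added to a stable stimulant*.

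The cost is an edit to the text and a more modest claim. The test, alpha, sample size (117 and 66 effective, 203 enrolled) and testing order do not change.
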